Protocol

**TITLE**: Dual benefits of Vaginal Estriol: improved urogenital health and re-myelination in relapsing remitting multiple sclerosis (RRMS)?

INVESTIGATORS:

- 1. [name]
- 2. [name]
- 3. [name]
- 4. [name]
- 5. [name]
- 6. [name], PhD

AIMS:

- 1. To evaluate the efficiency of vaginal estriol, as a treatment for urogenital symptoms in female patients with RRMS.
- 2. To evaluate the potential role of vaginal estriol in re-myelination in RRMS patients.

The goal of this pilot project is to determine the effectiveness of 1 mg transvaginal estriol, as an adjunctive therapy for female MS patients. Our goal is to recruit 20 patients from our MS clinic in the neurology department of Texas Tech University Health Sciences Center. This study has been planned in collaboration with reproductive endocrinology, endocrinology, gynecology and basic science. The 1mg transvaginal dose was chosen after careful search of the literature and consultation with our collaborators.

OBJECTIVES:

- Aim 1: Define if transvaginal estriol improves urogenital symptoms (urgency, frequency, intermittent incontinence), in female patients with Relapsing Remitting MS (RRMS). Bladder control scale, will be given at baseline, 3, 6, and 9 months after starting transvaginal estriol. Quality of life questionnaire will be given at baseline and at 9 months after starting vaginal estriol.
- Aim 2: Assess for evidence of re-myelination associated to the use of transvaginal estriol in woman with MS. Objective measurements for re-myelination will be quantified with brain MRI 3T, Optical coherence tomography (OCT)-and Visual evoked potentials (VEP).

INTRODUCTION / BACKGROUND / SIGNIFICANCE:

More than 2.3 million persons suffer from MS worldwide. Demyelination and axonal loss are the main pathological process in MS. Unfortunately remyelination occurs an incomplete fashion (Mallik, Samson, Wheeler-Kingshott, & Miller, 2014). Experimental models of MS have shown that preservation of myelin and remyelination of axons can increase neuronal survival. Until now, treatment for MS may decrease the relapse rate and progression, without any significant effect on remyelination.

Urinary issues in MS

Urinary dysfunction includes frequency, incontinence, frequent infections, occurs in about 80-90% of MS patients. It causes a major disruption in daily life, imposing economic burdens for patients and their families. Direct costs and indirect costs as psychological distress, loss of productivity are a significant burden for the patient, and increase the risk of unemployment.(Moore, 2001) Besides interfering with quality of life, urinary dysfunctions leads commonly to urinary tract infections which can have a direct impact on MS, worsening neurologic symptoms, and increasing in the number of relapses, which may lead to disability.

Estriol for urogenital health

Urinary dysfunction is frequently treated with antimuscarinic agents; side effects from these drugs (dry mouth, blurred vision, constipation and difficulty with micturition) make compliance an issue (David et.al). Transvaginal estriol decreases urinary symptoms and prevents urinary tract infections.(Rahn et al., 2014) There is less risk of endometrial hyperplasia and endometrial cancer with estriol treatment compared with estradiol treatment (Cody, Jacobs, Richardson, Moehrer, & Hextall, 2012). Furthermore, vaginal delivery offers regional benefits to the lower urogenital tract, it is well absorbed and it is not associated with entero-hepatic recirculation as oral estriol, as some of the adverse effects of oral estrogens are to produce an increase in thromboembolic events. (Rahn et al., 2014)

Estriol in MS, role in remyelination

Estriol is one of the three main estrogens, produced by fetal placenta. Levels increase significantly in the third trimester of pregnancy. It has been postulated as a possible neuromodulator and neuroprotective therapy in multiple sclerosis. (Tiwari-Woodruff & Voskuhl, 2009). Estriol has been studied in animal models and has been demonstrated to have distinctly different modulatory actions on the immune system than estradiol. Moreover, in 1-chloro-2, 4-dinitrobenzene (DNCB) induced contact dermatitis, estriol (Cody, Jacobs, Richardson, Moehrer, & Hextall, 2012)had the strongest suppressive effect when compared to estrone and estradiol (Cody et al., 2012). It has been reported that MS patients have a decreased annualized relapse rate during pregnancy, with a statistically significant decrease in the third trimester. Additionally, in the 3 months postpartum, the rate of relapse increases significantly. (Avila-Ornelas, Avila, Stosic, & Robles, 2011) This effect may be mediated at least in part by estriol, which rises during the third trimester of pregnancy and then falls precipitously postpartum. Furthermore, Estriol has been shown to have a positive effect reducing active brain lesions in multiple sclerosis. Estriol may have a role in remyelination.(Harlow, Honce, & Miravalle, 2015) Oligodendrocytes are the myelinating cells of the CNS. The process of re- myelination represents a major form of plasticity in the brain, unfortunately this process is not complete, leading to partial remyelination in patients with MS. (Mallik et al., 2014) Previous studies have shown that pregnancy leads to an increase in oligodendrocyte precursor cells (OPC) proliferation, oligodendrocyte generation and the number of myelinated axons in the maternal CNS. (Tiwari-Woodruff & Voskuhl, 2009) If estriol favors remyelination, this could revolutionize current treatment options for MS patients.

Benefit of vaginal estriol

Oral estriol has been shown to produce a significant decrease in the relapse rate in MS patients(Voskuhl et al., 2016). One of the reasons why vaginal estriol has a better absorption is that oral estriol is associated with entero-hepatic recirculation, which prolongs exposure due to recycling. Furthermore, vaginal estrogen delivery has a regional benefit to the lower urogenital tract, and is well absorbed at a dose of 0.5 mg to 1 mg. In a systematic review of randomized trials comparing vaginal estrogens, it was concluded that the 1mg vaginal estriol, was superior to lower doses for the treatment of urogenital symptoms. (Rahn et al., 2014) In animal models, estriol demonstrated to have distinctly different modulatory actions on the immune system than other form of estrogens, such as estradiol. Vaginal estriol does not increased the risk for heart disease, stroke, or cancer. (Rahn et al., 2014) In summary, patients with RRMS may significantly benefit from estriol as an adjunctive therapy to MS, improving quality of life and restoring myelin

HYPOTHESIS:

Transvaginal estriol offers a safe adjunctive therapy for female MS patients, it improves urogenital symptoms as well as promotes remyelination.

METHODS:

Subjects: Patients with relapsing remitting MS and urogenital symptoms (frequency, urgency, frequent urinary tract infections, incontinence) will be invited to participate in the study. Enrollment will be during their scheduled clinic appointment. Patients will be screened by a member of the study team during their visits to see if they qualify, if so they will be invited to participate in the study.

The clinical trial will be explained to potential participants in detail, reviewing the objectives and methodology of the study. There will be adequate time allotted to answer any questions or concerns from the potential participants. Those patients interested in participating in the study will be asked to sign the consent form. In order to remind patients about their follow-up visits, lab work, etc., they will be contacted routinely. Participants will be instructed to call in case of questions or concerns. Patients will be evaluated clinically during their scheduled follow up. Patients will be instructed by the primary investigator how to correctly use the vaginal cream. This will be done at their enrolment and reinforced by the principal investigator, during their follow up visits.

Inclusion criteria:

- 1. Female patients with RRMS between the ages of 35 to 65.
 - A) Being prescribed vaginal estriol to treat their urogenital symptoms.
 - B) Patients that had underwent menopause or surgical hysterectomy.
- 2. Patients will continue their disease modifying agent for MS during the trial.

Exclusion criteria:

- 1. Patients with personal history of breast cancer, uterine or ovarian cancer.
- 2. Patients with history of fibrocystic breast disease, heart attack or stroke.
- 3. Patients with history of thromboembolism.
- 4. Patients with progressive multiple sclerosis
- 5. Patients who are unable to undergo an MRI
- 6. Males
- 7. Patient is already on vaginal or oral or transdermal estrogens
- 8. Pregnant or breast-feeding patients
- 9. Patient taking sex hormones eg testosterone for libido
- 10. Patients taking DHEA or OTC related products that could influence the hormonal milieu.
- 11. Patient with prolapse uterus or conditions that would impact on transvaginal absorption of estriol

Enrollment in the study will be timed to their follow up brain MRI which will be performed as standard of care. Patients that have no baseline MRI or are unable to undergo MRI will be excluded from the study.

Site of study: The TTUHSC department of Neurology, MS clinic, Lubbock, TX; The TTUHSC Department of Ophthalmology and Visual Sciences, Lubbock, TX

Design:

This is a single-group prospective repeated-measures pilot trial. Duration is 12 months

Intervention:

Estriol vaginal cream will be formulated by Twin Oaks Pharmacy's compounding pharmacy, Regional Pharmacy, by the same compound specialist. 30 mg estriol powder will be mixed with 5 mL of propylene glycol and 22 g of vaginal base cream. The product can be stored at room temperature and has a shelf life of up to 4 months. It comes with an applicator.

The 1 mg dosing was chosen due to evidence in previous trials, and a systematic review of randomized trials comparing vaginal estrogens. It was concluded that the 1mg vaginal estroid, was superior to lower doses for the treatment of urogenital symptoms. (Rahn et al., 2014).

Study visits/Roles of subjects:

Initial visit:

After the informed consent has been obtained and all questions have been addressed Potential participants will be screened to ensure they are eligible for the clinical trial. Once eligibility has

been verified

- 1. Blood will be collected for baseline laboratory studies serum estriol, FSH and LH level. (about 20 ml of blood)
- 2. Baseline urogenital status will be evaluated by
 - Bladder Control Scale (BLCS) questionnaire
- 3. Multiple Sclerosis Quality of Life-54 (l-54) questionnaire will be completed
- 4. Baseline Visual Evoked Potential (VEP) within 4 weeks of Initial Visit
- 5. Optical Coherence Tomography (OCT) (occurs at the Ophthalmology clinic) within 4 weeks of Initial Visit
- 3 Tesla brain MRI will be performed as well. (within 3 months of initial visit)
- Dispense vaginal estriol cream once all baselines are complete

The primary investigators will instruct how to correctly use vaginal cream. Patients will be instructed to draw 1 mg of estriol vaginal cream with the applicator and apply intravaginally. They will be instructed to lay on their back for 30 min after vaginal cream application once a day for the duration of the study. The applicator is reusable, cleaning technique will also be given to the patient during their visit and reinforced during follow up. The applicator will be washed with regular soap and water and let air dry.

Patients will be instructed not to start applying vaginal cream until baseline lab work and imaging has been performed.

Three-month visit (90 days +/- 10 days):

- BLCS questionnaire will be completed
- Blood will be collected for serum estriol, FSH and LH level. (about 20 ml of blood)
- VEP and OCT will be also performed. ± 3 weeks of 3 month Visit
- Dispense vaginal estriol cream

Six-month visit (180 days +/- 10 days):

- BLCS questionnaire will be completed
- Blood will be collected for serum estriol, FSH and LH level. (about 20 ml of blood)
- VEP and OCT will be also performed. ±-3 weeks of 6 month Visit
- Dispense vaginal estriol cream

Nine-month visit (270 days +/- 10 days-FINAL VISIT):

- BLCS and MSQOL-54 questionnaires will be completed
- Blood will be collected f serum estriol, FSH and LH level. (about 20 ml of blood)
- 3 Tesla brain MRI will be repeated. \pm 3 months of 9 month Visit

During each visit patients will be questioned for adverse events, patients will also have a number to call in case of questions, concerns or adverse events.

Due to the nature of RRMS there might be acute exacerbations in which the patient will be treated with IV methylprednisolone 1gm a day x 3 to 5 days, this is the standard of care for MS exacerbations.

Schedule of events

Procedures	Screening visit	3 month visit	6 month visit	9 month visit FINAL VISIT
Date				
ICF	Х			
1&E	Х			
Blood work	x	x	x	x
BLCS	x	x	x	x
questionnaire				
MSQOL-54	x			x
questionnaire				
VEP (4 week	x	x	x	
window for				
screening visit or 3				
week window for 3				
and 6 month visits)				
OCT (4 week	x	x	x	
window for				
screening visit or 3				
week window for 3				
and 6 month visits))				
MRI variables (3	x			X
month window)				
Vaginal cream	x			
instructions				
Vaginal cream	х	x	x	
dispensing (once				
baselines				
complete)				
Compliance of		x	x	x
vaginal cream use				

Materials, instruments or measurements:

Urogenital measurements:

- Bladder control scale (BLCS) questionnaire (validated and used for evaluation of MS bladder symptoms. {Turnbull et al, 1992}). Raw scores on the 4 items are summed to create a Bladder Control Scale (BLCS) total score. Scores can range from 0-22, with higher scores indicating greater bladder control problems. See attached document. TEXAS TECH UNIVERSITY HEALTH SCIENCES CENTER

Quality of life:

- Quality of life questionnaire (Multple Sclerosis Quality of Life-54 {MSQOL-54}. Validated and widely used for MS patients. (Vickrey et al, 1995) (Vickrey et al, 1997). The questionnaire includes 54 questions that provide scores on physical and mental health status. Both scores can range 0-100. See attached document.

Blood work:

Levels of estriol, FSH, LH will be performed in Texas Tech Health Science Laboratory ([name] certified lab). The assay used will be the Beckman Coulter Access 2 immunoassay system analyzer. This will be run by an established OB/GYN hormone laboratory under the supervision of [name] and [name].

Re-myelinating measurements:

• Visual evoked potential (VEP) (measurement of the electrical signal recorded at the scalp over the occipital cortex in response to light stimulus) VEP/Prolongation of the P100 latency, is an indirect tool for remyelination in MS. (The test is non-invasive, patients will be looking at a checkboard pattern while the technician is measuring the time it takes to register the image to the brain cortex. This is achieved with scalp electrode in the posterior region.)

• 3Tesla brain MRI (performed as standard of care with no extra cost) will be evaluated for possible changes in white matter lesions, and Diffusion Tensor Imaging (DTI). This will be read by an expert MD collaborator independent from primary investigator.

• Optical coherence tomography (OCT) (noninvasive scan of the retinal layer which provides morphology imagery of the ganglion cell layer which is frequently affected in MS) (Noninvasive test, duration of about 5 to 10 min to perform, patient has to stay still and focus on a small light while we take a picture of the retina layer with the device.)

Data Sheet: A spreadsheet is attached. We will be gathering demographic data, MRI information, EDSS score, and electrophysiologic information, for details please see the spreadsheet attached.

Outcome variables:

1- Urogenital symptoms such as frequency, incontinence, frequent urinary tract infections, and BLCS questionnaire scores.

2- Remyelination (measured by brain MRI 3 DTI, other measurements include presence of T2 lesions, Flair lesions, DWI, T1 black hole, and DTI; Optical coherence tomography (OCT); and visual evoked potentials (VEP).

3- Quality of life, assessed using MSQOL-54 questionnaire.

Analysis:

Patient characteristics will be summarized using frequency (percentage) for categorical variables, and mean (SD) or median (interquartile range) for numerical variables as appropriate. Changes in blood work variables during the course of the study will be assessed using one-way repeated-measures analysis of variance (ANOVA). Compliance assessments will be used as covariate to adjust the differences if necessary, using an analysis of covariance model (ANCOVA). Urinary symptoms, and quality of life data will be analyzed using mixed-effects linear or logistic regression models for continuous or binary outcomes respectively. These models will account for the effect of estriol over time, compliance with treatment, and relevant patient characteristics.

Justification for Sample size:

This is a pilot study. We are planning to include 20 patients. Each patient will be their own control in a single-group repeated measures design. Assuming a significance level $\alpha = 0.05$, and power 1- $\beta = 0.80$, a

TEXAS TECH UNIVERSITY HEALTH SCIENCES CENTER IRB NUMBER: L19-020 IRB APPROVAL DATE: 12/13/2019

sensitivity power analysis determined that a moderate effect size (d=0.53 to d=0.66) would be required to detect statistically significant changes in the main outcome.

Risks

Studies suggest that when the lower-potency estrogen, estriol, is administered transvaginal, it does not increase the risk of hormone-dependent cancers of the breast or endometrium (uterine lining) Therefore the risk of breast and endometrial cancer is not increased with vaginal estriol. (Voojis et.al) Another safety concern of estrogens is the risk of thromboembolism. There is a paucity of prospective studies specifically looking at estriol and thromboembolism. Studies have shown that transdermal and transvaginal estrogen have a lower rate of thromboembolism. (Scarabin, Oger, & Plu-Bureau, 2003). Risks associated with venipuncture for blood draws include: discomfort, pain, bleeding, bruising, infection where the needle enters the skin; feeling lightheaded or fainting at the site of the needle or blood. No physical risk with VEP or OCT, these are noninvasive procedures.

Using the applicator or cream may cause vaginal discomfort or infection. Patients will be asked during their visits about vaginal discomfort or vaginal infections. Patients will also be encouraged to call if they are experiencing these. If the patient does experience these symptoms they may be referred to their PCP or Gynecologist for appropriate management.

Benefits:

Patients may experience improvement of her urogenital symptoms as well as improvement in their MS symptoms. Patient may have improved sexual function. Subjects could share satisfaction from potential benefits to other MS patients. May help revolutionize treatment of MS along with urogenital benefits at low cost

Confidentiality:

Patient's information will be de-identified and identifier information will be kept in a safe place. Electronic files will be locked by password which will be known by the principal investigator. Study documents will be kept at least 3 years then destroyed.

Study is registered at clinicaltrials.gov

Monitoring

To ensure compliance of the study protocol, GCP guidelines, and TTUHSC Human Research Protection Program research policies and procedures during the conduct of the study, a monitor in the Clinical Research Institute will conduct the monitoring of the study. The first monitoring visit will be conducted within two weeks after the first subject has been enrolled into the study. The succeeding monitoring visits will be scheduled periodically, but no less than every 2 months when there is an active study participant, at a mutually agreed timeframe by the PI and study monitor. All data collected will be 100% source document verified. The study monitor may inspect and audit all study documents, i.e. data collection forms, questionnaires, drug accountability, and medical records within the applicable confidentiality regulations.

Reimbursement:

No reimbursement for the participants

Funding: Laura W. Bush Institute for Women's Health and University Medical Center Women's Health Research Scholar Fund and the TTUHSC Department of Neurology.

Acknowledgements:

The investigators would like to express our sincere gratitude to the Clinical Research Institute and Department of Neurology at TTUHSC, Lubbock, Texas for assistance.

References:

- Cody, J. D., Jacobs, M. L., Richardson, K., Moehrer, B., & Hextall, A. (2012). Oestrogen therapy for urinary incontinence in post-menopausal women. In *Cochrane Database of Systematic Reviews*. https://doi.org/10.1002/14651858.CD001405.pub3
- Harlow, D. E., Honce, J. M., & Miravalle, A. A. (2015). Remyelination therapy in multiple sclerosis. *Frontiers in Neurology*, 6(DEC), 1–13. https://doi.org/10.3389/fneur.2015.00257
- Moore, K. H. (2001). The costs of urinary incontinence. *Medical Journal of Australia*, 174(9), 436–437. https://doi.org/10.2165/00019053-199406020-00009

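### The goal, Aim 1, the hypothesis and the model label claim an effect of estriol that a single-group before-after study of 20 women cannot show

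*Combined protocol and SAP*

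**What the plan says.** The Aims section gives the purpose: "The goal of this pilot project is to determine the effectiveness of 1 mg transvaginal estriol, as an adjunctive therapy for female MS patients". Aim 1 under Objectives is to establish whether estriol improves urogenital symptoms. The Hypothesis says of estriol that "it improves urogenital symptoms as well as promotes remyelination". The second aim is softer: it speaks of a potential role, and of evidence of remyelination associated with estriol use.

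Under Design: "This is a single-group prospective repeated-measures pilot trial". Under Justification for Sample size: "We are planning to include 20 patients" and "Each patient will be their own control in a single-group repeated measures design". No placebo, concurrent control, run-in or repeated baseline is described.

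The Methods invite women who have urogenital symptoms, and inclusion criterion 1A adds "Being prescribed vaginal estriol to treat their urogenital symptoms". There is no cut-off on the Bladder Control Scale (BLCS). The BLCS is a patient questionnaire given at baseline and at 3, 6 and 9 months. Under Analysis, urinary symptoms and quality of life go into mixed-effects models, of which the plan says: "These models will account for the effect of estriol over time".

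**The concern.** An effect of estriol is the difference between what happens with it and what would have happened without it. The plan observes only the first. Every woman receives the cream after baseline and is told to use it daily, so the average change since baseline is all that the model can estimate. Calling that change the effect of estriol gives the design a property it lacks, and so does calling each woman her own control.

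Several things other than estriol can lower a BLCS score over nine months: expectation in women who know they are treated, the natural course of a relapsing disease, changes in other care, and regression to the mean in women chosen because they had symptoms. Other care can change because exacerbations are treated with steroids during the study and the eligibility criteria do not restrict other bladder treatment. The plan mentions none of these as an explanation for change. As worded, a significant fall would be reported as estriol working, and an improvement in VEP or diffusion imaging as estriol-induced remyelination.

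**Working it through.** **1. Claim against design.** This step needs no assumption. The claim is causal (goal, Aim 1, Hypothesis, model label). The comparison is one group with its own single baseline. The plan contains no contrast between treated and untreated women, or between treated and untreated periods with more than one untreated measurement. Treatment that is not blinded is an inference from the single group and the absence of a placebo, but a safe one.

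**2. The plan's own figure.** The plan states that, with 20 patients, α = 0.05 (sidedness not given) and power 0.80, the detectable effect is d = 0.53 to 0.66. A two-sided paired t-test with n = 20 (noncentral t) gives 0.66, the upper end. The same test has power 0.61 at d = 0.53 and would need n = 30. A four-visit repeated-measures ANOVA with an assumed correlation of 0.5 gives 2f = 0.54, close to the lower end. The range is therefore attainable, but the plan should say which test gives 0.53.

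**3. How large could regression to the mean be on BLCS?** The documents give no BLCS SD, no test-retest correlation and no entry threshold, so the following are assumptions:
- baseline and follow-up scores are bivariate normal with equal means and SDs, correlation r, and no drug effect;
- entry takes the worst fraction p on the baseline score.

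Formulas, in population SD units:
- cut-off c = Φ⁻¹(1 − p); mean excess of enrolled women D = φ(c)/p; their baseline variance V = 1 − D(D − c);
- mean fall = (1 − r)D; variance of change = (1 − r)²V + 1 − r²;
- d_z = mean fall / SD of change.

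The only figure in the documents that bears on p is the 80-90% of MS patients with urinary dysfunction (Background).
- p = 0.9, r = 0.8: D = 0.1755/0.9 = 0.195; V = 0.712; fall 0.2 × 0.195 = 0.039; SD √(0.04 × 0.712 + 0.36) = 0.623; d_z = 0.06.
- p = 0.8, r = 0.5: D = 0.280/0.8 = 0.35; V = 0.583; fall 0.5 × 0.35 = 0.175; SD √(0.25 × 0.583 + 0.75) = 0.946; d_z = 0.18.
- p = 0.4, r = 0.5: D = 0.3863/0.4 = 0.966; V = 0.312; fall 0.483; SD √(0.25 × 0.312 + 0.75) = 0.910; d_z = 0.53.

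| Entry takes | r = 0.8 | r = 0.7 | r = 0.5 |
|---|---|---|---|
| 90% | 0.06 | 0.08 | 0.10 |
| 80% | 0.11 | 0.14 | 0.18 |
| worst 50% | 0.26 | 0.32 | 0.44 |
| worst 40% | 0.32 | 0.40 | 0.53 |
| worst 30% | 0.38 | 0.48 | 0.64 |

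To reach 0.53, entry must be limited to about the worst 40% at r = 0.5, 33% at 0.6, 24% at 0.7 or 14% at 0.8.

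Two variations matter. Averaging the three follow-ups raises the range for 80-90% entry from 0.06-0.18 to 0.08-0.23. If entry rests on a complaint that correlates only 0.5 to 0.7 with BLCS (worst 30%, r = 0.6), d_z is 0.26 to 0.38.

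**4. What that does to a test.** With n = 20 and a two-sided 5% paired t-test, the nominal chance of a significant improvement from an inert cream is 2.5%. At d_z = 0.06 it is about 4.5%, and at d_z = 0.18 about 12%. Expectation would add to this; the documents give no figure for it.

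**The case against.** **The stronger reading.** A reader might infer that regression to the mean alone could produce the effect the trial is planned to detect. The documents do not support that. It needs a mean BLCS about 1 SD above the clinic population, roughly the worst 38%, together with a low correlation. No BLCS threshold is set, women are chosen on symptoms and a prescription rather than on the score, and enrolment follows a scheduled appointment timed to a routine MRI, not a symptom peak. On the other side, the prevalence figure counts any urinary dysfunction, and requiring a prescription may select more strongly, by an amount nobody can state. So the large values are possible but not shown.

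**Aim 2.** A reader might carry the same argument over to remyelination. Women are not selected on VEP, OCT or MRI, so it does not apply there. These measures are not self-reported, the MRI is read independently of the primary investigator, and Aim 2 is already worded as association. Nor does the background's remark that remyelination is incomplete predict net improvement over nine months. What remains is the missing control and a hypothesis that still says estriol promotes remyelination.

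**Exposure data.** The models include compliance, and serum estriol is measured at every visit, so exposure does vary between women. That variation is not randomised and does not supply a control.

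**It is a pilot.** The design is openly described and the title ends in a question mark. But the word pilot is attached to an effectiveness goal and to power for significant change. No feasibility objective, no variance-estimation objective and no later controlled trial is mentioned.

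**Conclusion.** The wording is wrong as written, and this follows from the text alone: the goal, Aim 1, the hypothesis and the model label claim a causal effect that one uncontrolled group of 20 cannot show. The conclusion does not depend on the size of regression to the mean, because expectation, natural course and other care cannot be separated from treatment in any case.

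Regression to the mean on BLCS is one contributor of unknown size. It is small if entry mirrors the documents' prevalence and comparable with the planned effect only under strong selection on the score and low correlation. Both inputs are assumptions. For VEP, OCT and MRI the point is limited to the absence of a control.

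**What to change.** - **Aims, Objectives (Aim 1) and Hypothesis:** restate as estimating within-patient change during estriol use, with confidence intervals, in order to plan a controlled trial. Aim 2 can stay in its associational form; the remyelination half of the Hypothesis should be brought into line with it.
- **Analysis:** replace the label for the time effect with *change over time during treatment*. Add that a statistically significant change will not be reported as proof of effectiveness or of estriol-induced remyelination.
- **Regression to the mean:** leave a calculation out, or present it only as illustration over stated ranges of both selection strength D and correlation r. Varying r alone gives no answer, because D needs a clinic-population BLCS mean and SD, which the plan does not collect.

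The cost is a few sentences. It adds no patients, visits or procedures and does not touch treatment. The downside is a more modest claim.

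### MSQOL-54 is taken only at baseline and month 9 with no early-exit assessment, so the planned mixed model rests on an unstated missing-data assumption that the schedule cannot support

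*Combined protocol and SAP*

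**What the plan says.** Three places in the protocol agree on when quality of life is measured.

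- OBJECTIVES, Aim 1: "Quality of life questionnaire will be given at baseline and at 9 months after starting vaginal estriol". The same paragraph gives the bladder scale (BLCS) at baseline and months 3, 6 and 9.
- Study visits: the initial visit lists "Multiple Sclerosis Quality of Life-54 (l-54) questionnaire will be completed". The three- and six-month visits list BLCS but not MSQOL-54. The last visit, "Nine-month visit (270 days +/- 10 days-FINAL VISIT", lists "BLCS and MSQOL-54 questionnaires will be completed".
- Schedule of events: MSQOL-54 is marked at screening and month 9 only. The table has no early-exit column.

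Quality of life is the third listed outcome: "Quality of life, assessed using MSQOL-54 questionnaire". Under Analysis, "quality of life data will be analyzed using mixed-effects linear or logistic regression models", and "These models will account for the effect of estriol over time, compliance with treatment, and relevant patient characteristics". The sample size section says "We are planning to include 20 patients", in a single group with each patient as her own control. The documents give no dropout allowance, withdrawal procedure, analysis population or missing-data method.

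**The concern.** A patient who leaves after month 3 or month 6 has attended the clinic on treatment and completed BLCS, yet she contributes no quality-of-life value after baseline. For BLCS, the mixed model can use her interim scores to inform what month 9 would have been. For MSQOL-54 it has only her baseline.

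If patients leave because their quality of life has fallen since baseline, the model has no record of the fall. It fills in their month 9 from the relation between baseline and month 9 seen in those who stayed, and the estimated change comes out too favourable. With one open-label group, no comparator would show that this had happened. The loss is built into the data collection and cannot be repaired at analysis.

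**Working it through.** **1. The plan's own figure.** The sample size section gives d = 0.53 to 0.66 for 20 patients, alpha 0.05 and power 0.80. A two-sided paired t-test with n = 20 gives d = 0.66, the upper end. A four-measure repeated-measures ANOVA (assumed correlation 0.5, sphericity) gives f = 0.27, so d = 2 × 0.27 = 0.54, close to the lower end. MSQOL-54 has two measurements, so 0.66 is the figure that applies to it.

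**2. Precision if patients are lost (dropout assumed).** Detectable d for a paired comparison, with power at d = 0.66 in brackets:

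- n = 20: 0.66 (80%)
- n = 18: 0.70 (75%)
- n = 16: 0.75 (69%)
- n = 14: 0.81 (63%)

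**3. What the mixed model does with a baseline-only patient.** With two time points and month 9 missing for leavers, the maximum-likelihood estimate is

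change = (mean change in stayers) − (1 − b) × (baseline mean of all − baseline mean of stayers),

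where b is the slope of month 9 on baseline among stayers. Leavers enter only through their baseline.

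**4. When that is enough and when it is not.** Large-sample illustration with true change 0.30 SD, 20% dropout and baseline-to-month-9 correlation 0.4 / 0.6 / 0.8:

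| Exit depends on | Stayers' mean change | Two-point mixed model |
|---|---|---|
| nothing (random) | 0.30 / 0.30 / 0.30 | 0.30 / 0.30 / 0.30 |
| baseline quality of life | 0.20 / 0.23 / 0.27 | 0.30 / 0.30 / 0.30 |
| the unseen month-9 value | 0.41 / 0.37 / 0.33 | 0.45 / 0.42 / 0.37 |

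**5. Exit after a poor month 6.** Assume true changes of 0.1, 0.2 and 0.3 SD at months 3, 6 and 9, and that the lowest 20% on the month-6 value, or on the change to month 6, leave after that visit. Correlations are exchangeable (0.4, 0.6, 0.8) or autoregressive (0.8 per step). Cutting off the lowest 20% of a normal variable moves the stayers' mean up by 0.280/0.80 = 0.35 SD and leaves a variance of 1 − 0.842 × 0.35 − 0.35² = 0.583, a reduction of 0.417.

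- Lowest result (exchangeable 0.8, selection on month-6 value). Stayers' baseline and month 9 both rise by 0.8 × 0.35 = 0.28, so their mean change is 0.30. b = (0.8 − 0.64 × 0.417)/(1 − 0.64 × 0.417) = 0.533/0.733 = 0.727. Estimate = 0.30 + (1 − 0.727) × 0.28 = 0.38.
- Highest result (autoregressive 0.8, selection on change to month 6). The correlations are 0.64 (baseline to month 6), 0.80 (month 6 to 9) and 0.512 (baseline to 9). The SD of the change to month 6 is √(2 × 0.36) = 0.849. Stayers' baseline moves by −0.36/0.849 × 0.35 = −0.149 and their month 9 by (0.80 − 0.512)/0.849 × 0.35 = +0.119, so their mean change is 0.30 + 0.119 + 0.149 = 0.57. b = (0.512 + 0.424 × 0.339 × 0.417)/(1 − 0.424² × 0.417) = 0.572/0.925 = 0.618. Estimate = 0.568 − (1 − 0.618) × 0.149 = 0.51.

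The remaining cases fall between these. The overstatement is 0.38/0.30 = 1.27 to 0.51/0.30 = 1.70, that is, roughly 25% to 70%. When the month-3 and month-6 values are in the model, the estimate is 0.30 in every case, because exit then depends on something observed.

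**The case against.** The strongest reply is that the plan does not propose a completers-only change score. It proposes a mixed model, which keeps baseline-only patients and is unbiased when exit depends on baseline quality of life (step 4). That stands. A reader might infer that the result describes completers only; the documents do not support this. Compliance is recorded at months 3, 6 and 9 and is a model term, so part of the exit process may be captured. Compliance is not quality of life, though, and the plan does not say that it is meant to serve this purpose.

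Second, the size is assumed. A reader might put k leavers with zero change into 20/(20 − k) and report an overstatement of 1.11 (k = 2) to 1.33 (k = 5). Those factors describe a raw completer mean under an invented k, and that mean is not the planned estimate. The direction is not fixed for a completer mean either: with baseline-driven exit it understates the change (0.20 to 0.27 against 0.30).

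Third, the documents do not say that discomfort, infection or relapse leads to withdrawal. The Risks section speaks of referral, and the visits section of standard treatment for exacerbations. Nothing says that stopping the cream means leaving the study. So it is plausible, but not documented, that those who do badly are those who leave.

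Fourth, a two-point schedule for a 54-item form is a defensible choice on burden in a 20-patient pilot where quality of life is the third outcome. Nor is the wording about effects over time an error: the sentence covers BLCS and MSQOL-54 together, and two points still give a time effect.

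What survives is that validity depends on a missing-at-random assumption which the plan does not state and for which the schedule collects little supporting data.

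**Conclusion.** The point holds as a weakness in data collection. Followed exactly, the plan yields no quality-of-life value after baseline from anyone who leaves before month 9. The mixed model is then valid only if exit depends on baseline quality of life or modelled covariates. If exit follows a later decline, the estimate is biased upward.

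The size for this trial is unknown, since no dropout rate is given. The 0.38 to 0.51 SD against a true 0.30 is an illustration that rests on 20% dropout, exit governed entirely by month-6 status, normal scores and the listed correlations. It is not a forecast. With no dropout, random dropout or baseline-driven dropout, the two-point model is not biased.

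The change is worth making because it is cheap. It does not threaten the bladder outcome's schedule, which already has interim values.

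**What to change.** - Add MSQOL-54 to the existing month-3 and month-6 visits. If the burden is judged too great, collect it at least at exit.
- Add an early-exit column to the Schedule of events, in which a patient leaving the study completes BLCS and MSQOL-54.
- State that a patient who stops the cream but remains in the study continues with the scheduled assessments.
- Under Analysis, fit the planned mixed model to all MSQOL-54 values, including those after stopping the cream, and state that it assumes data missing at random given the observed values and covariates.
- Add a simple sensitivity analysis for early leavers: for example, set their month-9 change to zero, then to progressively worse values, and report where the conclusion alters.
- Report how many patients left, when and why.

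Cost: up to two more self-completed 54-item questionnaires per patient at visits already attended, one exit contact, a table edit and a few sentences of analysis text. The downside is response burden. A limit also remains: an exit or month-6 value is not a month-9 value, so bias from deterioration after the last assessment is reduced but not removed, which is why the sensitivity analysis is needed as well.
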